24.2 Appendix 2: Sample List of Excluded or Cautionary Medications

Strong CYP3A inducers - Carbamazepine, enzalutamine, mitotane, phenytoin, rifampin, St. John's Wort

Moderate CYP3A inducers - Bosentan, efavirenz, etravirine, modafinil

Strong CYP3A inhibitors - Boceprevir, clarithromycin, cobicistat, danoprevir/ritonavir, elvitegravir/ritonavir, idelalsib,* indinavir, itraconazole, ketoconazole, mibefradil, lopinavir/ritonavir, nefazodone, nelfinavir, paritaprevir/ritonavir combinations, ritonavir, posaconazole, saquinavir, telaprevir, telithromycin, tipranavir/ritonavir, troleandomycin, voriconazole

Moderate CYP3A inhibitors - Aprepitant, cimetidine, ciprofloxacin, conivaptan, crizotinib,* cyclosporine, diltiazem, dronedarone, erythromycin, fluconazole, fluvoxamine, imatinib,* tofisopam, verapamil

Warfarin and coumarin derivatives (e.g., phenprocoumon)**

P-gp substrates - Aliskiren, ambrisentan, colchicine, dabigatran etexilate, digoxin, everolimus,* fexofenadine, lapatinib,* loperamide, maraviroc, nilotinib,* ranolazine, saxagliptin, sirolimus,* sitagliptin, talinolol, tolvaptan, topotecan*

BCRP substrates - Methotrexate,* mitoxantrone,* irinotecan,* lapatinib,* rosuvastatin, sulfasalazine, topotecan*

OATP1B1/1B3 substrates - Asunaprevir, atrasentan, atorvastatin, cerivastatin, danoprevir, ezetimibe, fexofenadine, fluvastatin, glyburide, rosuvastatin, simvastatin acid, pitavastatin, pravastatin, repaglinide, telmisartan, valsartan, olmesartan **P-gp inhibitors** - Amiodarone, captopril, carvedilol, felodipine, propafenone, quercetin, quinidine, ranolazine, ticagrelor

Note that this is not an exhaustive list. For an updated list, see the following link:

<https://www.fda.gov/drugs/development-resources/drug-interactions-labeling>

In addition to the medications listed in this table, subjects receiving venetoclax should not consume grapefruit, grapefruit products, Seville oranges (including marmalade containing Seville oranges) or Star fruits within 3 days prior to each cycle and while on venetoclax.

* These are anticancer agents; consult Investigator Coordinator before use.

** Closely monitor international normalized ratio (INR).

24.3 Appendix 3: Contraception Recommendations

While participating in this research study, female subjects should not become pregnant or breastfeed a baby.

If female, subject must be either postmenopausal or permanently surgically sterile (refer to inclusion criteria for definitions of both) OR a female of childbearing potential, practicing at least one of the following highly effective methods of birth control, on Study Day 1 (or earlier) through at least 30 days after the last dose of venetoclax or at least 3 months after the last dose of azacitidine.

- Combined (estrogen and progestogen containing) hormonal contraception (oral, intravaginal, transdermal) associated with the inhibition of ovulation, initiated at least 1 month prior to Study Day 1.
- Progestogen-only hormonal contraception (oral, injectable, implantable) associated with inhibition of ovulation, initiated at least 1 month prior to Study Day 1.
- Bilateral tubal occlusion/ligation at least 1 month before study participation.
- Bilateral tubal occlusion via hysteroscopy (e.g., Essure®), provided a hysterosalpingogram confirms success of the procedure at least 1 month before study participation.
- Vasectomized partner(s), provided the vasectomized partner verbally confirms receipt of medical assessment of the surgical success, and is the sole sexual partner of the Female subjects of childbearing potential (trial participant).
- Intrauterine device (IUD).
- Intrauterine hormone-releasing system (IUS).
- True abstinence: Refraining from heterosexual intercourse when this is in line with the preferred and usual lifestyle of the subject (periodic abstinence [e.g., calendar, ovulation, symptothermal, post-ovulation methods] and withdrawal are not acceptable).

If required per local practices, male or female condom with or without spermicide OR cap, diaphragm or sponge with spermicide should be used in addition to one of the birth control methods listed above (excluding true abstinence).

Male subjects who are sexually active with a female of child-bearing potential, must agree to use effective contraceptive measures as defined in the protocol for female study subjects of childbearing potential from Study Day 1 through at least 30 days after the last dose of venetoclax or at least 3 months after the last dose of azacitidine, whichever is later.

Male subjects should be advised to not donate or store sperm from Study Day 1 through at least 3 months after the last dose of azacitidine.

24.4 Appendix 4: CTCAE Version 5.0

Toxicity will be scored using CTCAE Version 5.0 for toxicity and adverse event reporting.

[HTTPS://CTEP.CANCER.GOV/PROTOCOLDEVELOPMENT/ELECTRONIC_APPLICATIONS/DOCS/CTCAE_V5_QUICK_REFERENCE_8.5X11.PDF](https://ctep.cancer.gov/protocoldevelopment/electronic_applications/docs/ctcae_v5_quick_reference_8.5x11.pdf)

CTCAE V 5.0.pdf

Article last updated on: November 27, 2017.

All Study sites will have access to a copy of the CTCAE Version 5.0.

24.5 Appendix 5: Eastern Cooperative Oncology Group (ECOG) Performance Status Grading

Grade	Performance Status
0	Fully active, able to carry on all pre-disease performance without restriction
1	Restricted in physically strenuous activity but ambulatory and able to carry out work of a light or sedentary nature, e.g., light house work, office work
2	Ambulatory and capable of all selfcare but unable to carry out any work activities. Up and about more than 50 % of waking hours
3	Capable of only limited selfcare, confined to bed or chair more than 50 % of waking hours
4	Completely disabled. Cannot carry on any selfcare. Totally confined to bed or chair
5	Dead

24.6 Appendix 6: Risk classification according to IPSS R

IPSS-R Cytogenetic risk groups

Cytogenetic prognostic subgroups	Cytogenetic abnormalities
Very good	-Y, del(11q)
Good	Normal, del(5q), del(12p), del(20q), double including del(5q)
Intermediate	del(7q), +8, +19, i(17q), any other single or double independent clones
Poor	-7, inv(3)/t(3q)/del(3q), double including -7/del(7q), Complex: 3 ≥ abnormalities
Very poor	Complex: >3 abnormalities

IPSS-R Prognostic Score Values

Prognostic variable	0	0.5	1	1.5	2	3	4
Cytogenetics	Very Good		Good		Intermediate	Poor	Very Poor
BM Blast %	≤ 2		> 2- < 5%		5-10%	> 10%	
Hemoglobin	≥ 10		8- < 10	< 8			
Platelets	≥ 100	50- < 100	< 50				
ANC	≥ 0.8	< 0.8					

IPSS-R Cytogenetic risk groups

RISK CATEGORY	RISK SCORE
Very Low	≤ 1.5
Low	$> 1.5 - 3$
Intermediate	$> 3 - 4.5$
High	$> 4.5 - 6$
Very High	> 6

24.7 Appendix 7: Risk classification according to IPSS

score (points)	marrow blasts	karyotype	cytopenias* (number of affected cell lines)
0.0	< 5	normal, -Y, del 5q, del 20q	0 - 1
0.5	5 - 10	other	2 - 3
1.0		complex (≥ 3 anomalies) and/or chromosome 7 anomalies	
1.5	11 - 20		
2.0	21 - 30		

***Definition for cytopenias:**

neutrophils	< 1800/ μ l
hemoglobin	< 10 g/dl
platelets	< 100 000/ μ l

type	points	median survival
low-risk:	0	about 5.7 years
intermediate-1-risk:	0.5 – 1.0	about 3.5 years
intermediate-2-risk:	1.5 – 2.0	about 1.2 years
high-risk:	≥ 2.5	about 5 months

24.8 Appendix 8: Tabulated summary of dyshematopoiesis

Dyshematopoiesis in bone marrow:	
Dyserythropoiesis	Ringed sideroblasts, megaloblastic transformation, nucleus fragmentation, more than one nucleus, nuclei not round, sideroblastosis, PAS-positive erythroblasts
Dysgranulopoiesis:	Increase of blasts, hypogranulated myelocytes, Auer rods, increase of monocytes, pseudo-Pelger-cells, myeloperoxidase-defect, increase of promyelocytes
Dysmegakaryopoiesis:	Micromegakaryocytes, mononuclear megakaryocytes, megakaryocytes with rounded, separate nucleus segments

24.9 Appendix 9: Groups according to FAB-classification

Subtype	Percentage of blasts blood bone marrow	Further changes
Refractory anemia (RA)	≤ 1 % < 5 %	
Refractory anemia with ringed sideroblasts (RARS)	≤ 1 % < 5 %	> 15 % ringed sideroblasts within erythropoiesis
Refractory anemia with excess of blasts (RAEB)	< 5 % 5-20 %	
RAEB in transformation (RAEB-T)	> 5 % 20-30 %	facultative Auer rods
Chronic myelomonocytic leukemia (CMML)	< 5 % 0-20 %	peripheral monocytosis (> 1000/μl)

24.10 Appendix 10: Groups according to WHO-classification 2016

Subtype	Dysplastic lines	Cytopenias	Ring sideroblasts (% of erythroid cells)	Blasts in BM and PB	Karyotype (conventional banding)
MDS-SLD	1	1 or 2	<15% / <5 % ²	BM <5%, PB <1% no Auer rods	All, except del(5q) ± 1 other non-chr 7 abnormality
MDS-MLD	2 or 3	1-3	<15% / <5 % ²	BM <5%, PB <1% no Auer rods	All, except del(5q) ± 1 other non-chr 7 abnormality
MDS-RS					
MDS-RS-SLD	1	1 or 2	<15% / <5 % ²	BM <5%, PB <1% no Auer rods	All, except del(5q) ± 1 other non-chr 7 abnormality
MDS-RS-MLD	2 or 3	1-3	<15% / <5 % ²	BM <5%, PB <1% no Auer rods	All, except del(5q) ± 1 other non-chr 7 abnormality
MDS with del(5q)	1-3	1 or 2	not relevant	BM <5%, PB <1% no Auer rods	Isolated del(5q) or with 1 other non-chr 7 abnormality
MDS-EB					
MDS-EB1	0-3	1-3	not relevant	BM 5-9% or PB 2-4% no Auer rods	not relevant
MDS-EB2	0-3	1-3	not relevant	BM 10-19% or PB 5-19% or Auer rods	not relevant
MDS-U (unclassifiable)					
with 1% blood blasts	1-3	1-3	not relevant	BM <5%, PB =1% no Auer rods	not relevant
with single lineage dysplasia and pancytopenia	1	3	not relevant	BM <5%, PB <1% no Auer rods	not relevant
based on defining cytogenetic abnormality	0	1-3	<15% ⁴	BM <5%, PB <1% no Auer rods	MDS-defining abnormality

1 cytopenias defined as hemoglobin < 100 g/L, Platelets < 100 x 10⁹/L, ANC <1.8 x 10⁹/L

2 if SF3B1 has a mutation

3 1 % peripheral blasts have to be judged at 2 different times

4 Cases with ≥ 15% of ring sideroblasts have (per definition) significant dyserythropoiesis and are therefore MDS-RS-SLD

24.11 Appendix 11: MDS response criteria

The following response criteria are based on the International MDS Working Group (IWG) 2006 Criteria for Measurement of Response/Treatment Effect in MDS by *Cheson et al.* [10].

24.11.1 Complete remission (CR)

Bone marrow evaluation: Bone marrow showing < 5% myeloblasts with normal maturation of all cell lines*. Persistent dysplasia will be noted*.

Peripheral blood[†] evaluation:

- Hemoglobin > 11 g/dL (untransfused, patient not on erythropoietin)
- Neutrophils $\geq 1.000/\text{mm}^3$ (not on a myeloid growth factor)
- Platelets $\geq 100.000/\text{mm}^3$ (untransfused, not on a thrombopoetic agent)
- Blasts – 0%

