9 CRITERIA FOR MEASUREMENT OF STUDY ENDPOINTS

9.1 Efficacy Outcome Measures

Primary Endpoint:

For MDS patients:

Overall response rate (ORR), defined as the proportion of patients who achieve a CR or PR per proposal for modification of the International Working Group (IWG) criteria for MDS, 2006 (Appendix 11):

1. CR is defined as bone marrow blasts $\leq 5\%$, without persistent dysplasia will be noted with normal maturation of all cell lines peripheral blood: Hgb ≥ 11 g/dL platelets $\geq 100 \times 10^9/L$, ANC $\geq 1.0 \times 10^9/L$, blasts 0%.
2. PR is defined as all CR criteria if abnormal before treatment except for bone marrow blasts decreased by $\geq 50\%$ over pretreatment but still $> 5\%$ cellularity.

For AML patients:

CR Rate, defined as the proportion of patients who achieve a CR per the ELN2017 criteria: CR is defined as BM blasts $< 5\%$, absence of circulating blasts and blasts with Auer rods, absence of extramedullary disease, ANC $\geq 1.0 \times 10^9/L$ (1,000/ μ L); platelet count $\geq 100 \times 10^9/L$ (100,000/ μ L).

Secondary Endpoints:

For MDS patients:

1. Overall improvement rate (OIR), defined as the proportion of patients reaching a CR, Marrow CR, PR, or hematologic improvement (HI) per proposal for modification of the IWG criteria for MDS, 2006 (Appendix 11). Marrow CR is defined as bone marrow blasts $\leq 5\%$ and decreased by 50% over pretreatment. Peripheral blood: if HI responses, they will be noted in addition to marrow CR. HI is defined as:
 - a. Erythroid response (pretreatment, < 11 g/dL) is defined as Hgb increase by ≥ 1.5 g/dL. Relevant reduction of units of red blood cells (RBC) transfusions by an absolute number of at least 4 RBC transfusions/8 weeks, compared with the pretreatment transfusion number in the previous 8 weeks. Only RBC transfusions given for a Hgb of ≤ 9.0 g/dL will count in the RBC transfusion response evaluation.
 - b. Platelet response (pretreatment $< 100 \times 10^9/L$) is defined as absolute increase of $\geq 30 \times 10^9/L$ for patients starting with $> 20 \times 10^9/L$ platelets, and an increase from $< 20 \times 10^9/L$ to $> 20 \times 10^9/L$ and by at least 100%.
 - c. Neutrophil response (pretreatment, $< 1.0 \times 10^9/L$) is defined as at least 100% increase and an absolute increase $> 0.5 \times 10^9/L$

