24.11.2 Partial remission (PR)

All of the CR criteria (if abnormal prior to treatment), except:

Bone marrow evaluation: Blasts decreased by $\geq 50\%$ over pretreatment but still > 5%. Cellularity and morphology are not relevant.

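### For MDS patients, section 9.1 and the Appendix 11 it cites define CR differently, so exactly 5% blasts with full blood recovery is CR by one text and neither CR nor PR by the other

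*Protocol*

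**What the plan says.** Section 9.1 sets the MDS primary endpoint as "Overall response rate (ORR), defined as the proportion of patients who achieve a CR or PR per proposal for modification of the International Working Group" criteria of 2006 and points to Appendix 11 for them. It then restates the criteria itself:

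- **CR:** marrow blasts at or below 5%; a dysplasia clause reading "without persistent dysplasia will be noted with normal maturation of all cell lines peripheral blood"; "Hgb ≥ 11 g/dL platelets" and neutrophil limits; no blood blasts. No transfusion or growth-factor condition is given.
- **PR:** "PR is defined as all CR criteria if abnormal before treatment except for bone marrow blasts decreased by" at least 50% from pretreatment while still above 5%, with the word cellularity attached to that limit.

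Appendix 11 reads differently:

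- **CR (24.11.1):** "Bone marrow showing < 5% myeloblasts with normal maturation of all cell lines"; "Persistent dysplasia will be noted"; haemoglobin above 11 g/dL, untransfused and not on erythropoietin; neutrophils without a myeloid growth factor; platelets untransfused and without a thrombopoietic agent.
- **PR (24.11.2):** all CR criteria if abnormal before treatment, except blasts decreased by at least 50% "over pretreatment but still > 5%. Cellularity and morphology are not relevant".
- **Marrow CR (24.11.3):** blasts at or below 5% and decreased by at least 50%.

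Section 9.1 counts marrow CR and haematologic improvement only in the secondary overall improvement rate. Section 10.2 defines overall response as CR, marrow CR, PR or haematologic improvement.

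**The concern.** The protocol gives two rules for classifying the same MDS patient on the primary endpoint and does not say which governs. Section 9.1 presents its criteria as those of Appendix 11, so a reader has no reason to expect a difference.

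The study is open label, with about 20 sites, and section 10.2 has the investigator assess efficacy. Two investigators could each follow the protocol and classify the same marrow differently. The phase II decision rests on small counts: 3 against 4 responses in the first 14 evaluable patients, then 13 or more at the end. A rule that is unclear at a boundary can move those counts, and if it is settled only after the data are seen, the choice can no longer be shown to be independent of the result.

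**Working it through.** **1. The two MDS definitions side by side**

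| Item | Section 9.1 | Appendix 11 |
|---|---|---|
| CR, marrow blasts | ≤ 5% | < 5% |
| CR, haemoglobin | ≥ 11 g/dL | > 11 g/dL |
| CR, transfusion and growth factors | not mentioned | untransfused; no erythropoietin, myeloid growth factor or thrombopoietic agent |
| CR, dysplasia | garbled; can be read as requiring its absence | recorded |
| PR, marrow blasts | fall ≥ 50%, still > 5% (cellularity) | fall ≥ 50%, still > 5%; cellularity not relevant |

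The transfusion and growth-factor row can matter in practice, because section 6.5 permits transfusion and G-CSF on study.

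**2. Classifying boundary patients**

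Assumptions: other counts met, normal maturation, no transfusion or growth factor, pretreatment haemoglobin abnormal.

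| Pretreatment blasts | Blasts now | Hgb (g/dL) | Section 9.1 | Appendix 11 |
|---|---|---|---|---|
| 8% | 5% | 11.1 | CR | neither CR, PR nor marrow CR |
| 10% or 18% | 5% | 11.1 | CR | marrow CR; neither CR nor PR |
| 18% | 4% | 11.0 | CR | marrow CR; not CR |
| 18% | 6% | 11.0 | PR | not PR |
| 18% | 4% | 11.1 | CR | CR |

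In the first two rows Appendix 11 leaves a gap: CR needs less than 5% and PR needs more than 5%. Marrow CR takes up exactly 5% only if blasts fell by at least half, that is, from 10% or more. In the fourth row the haemoglobin difference reaches PR, because PR inherits the CR blood limits.

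**3. What one patient is worth**

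The protocol states no figure on this point, so there is none to reproduce. Inputs: 14 + 16 = 30 patients and success at 13 or more responses (section 3). One patient is 1/30 = 3.3 percentage points of response rate.

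Reclassifying one patient upward changes the decision only if the count would otherwise be 12. Reclassifying one downward changes it only if the count would otherwise be 13. With X ~ Binomial(30, p) and P(X = k) = C(30, k) p^k (1 − p)^(30 − k):

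- p = 0.40: P(12) = 86,493,225 × 0.4^12 × 0.6^18 = 0.147; P(13) = 119,759,850 × 0.4^13 × 0.6^17 = 0.136.
- p = 0.50: P(12) = 86,493,225 / 2^30 = 0.081; P(13) = 119,759,850 / 2^30 = 0.112.

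These ignore the stage-1 stop. Including it (continue only with 4 or more of 14), the probability of success with the final cut at 12, 13 or 14 is:

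| True rate | Cut 12 | Cut 13 | Cut 14 | Effect of one response |
|---|---|---|---|---|
| 0.40 | 0.555 | 0.416 | 0.284 | 0.139 or 0.132 |
| 0.50 | 0.890 | 0.814 | 0.705 | 0.076 or 0.108 |

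The two calculations agree closely.

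**The case against.** **The affected group is limited and its size is unknown.** This stands. The AML definition of CR is blasts below 5% in both section 9.1 and Appendix 12, so only MDS patients are concerned. The protocol gives neither the MDS share of phase II nor the frequency of values at exactly 5% blasts or 11.0 g/dL. Every probability above is conditional on a boundary patient existing.

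**A larger effect is tempting but wrong.** A reader might add the chances of 12 and 13 responses (0.147 + 0.136 = 0.283 at 40%; 0.081 + 0.112 = 0.192 at 50%, rounded) and infer that one patient decides a fifth to a quarter of trials. The two cases need reclassification in opposite directions, so a given change acts on only one of them. Nor do the documents support treating exactly 5% as a common reading.

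**The dysplasia conflict is not a clear one.** A reader might infer that section 9.1 excludes patients whom Appendix 11 accepts. The section 9.1 sentence is ungrammatical and looks like a damaged copy of the appendix. Both texts require normal maturation of all cell lines, and a footnote to Appendix 11 says the normal range of dysplastic change should be considered. The sentence is ambiguous, not a firm exclusion. The stray word in the PR limit is likewise a copying fault.

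**Under section 10.2 part of the conflict disappears.** If overall response includes marrow CR, the patient at 5% whose blasts halved is a responder under either CR text. That is correct. However, section 9.1 is where the primary endpoint is defined, and it counts only CR and PR. Adopting the section 10.2 list would still leave two definitions of CR, of the separately reported CR rate, and of PR. A patient at 5% whose blasts fell by less than half is also not covered by marrow CR.

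**Conclusion.** The point holds for MDS patients. The two texts differ on the blast limit, the haemoglobin limit and the transfusion and growth-factor conditions, and nothing in the protocol ranks one above the other. Under the section 9.1 endpoint, exactly 5% blasts with full blood recovery is a response by one text and not by the other.

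Its effect on the trial cannot be quantified without the number of boundary patients. For one such patient moved in one direction, the decision at 13 of 30 changes with probability about 14 to 15% at a true rate of 40% and 8 to 11% at 50%, by a simple binomial that assumes 30 evaluable patients and no early stop. This is more than a clerical matter, because it affects the classification rule for an investigator-assessed primary endpoint. It does not show that the trial's result will be wrong.

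**What to change.** Before the interim look:

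1. Replace the CR and PR wording in section 9.1 with the Appendix 11 text that it cites, so that one definition governs. Include the transfusion and growth-factor conditions and one sentence on whether persistent dysplasia prevents CR or is only recorded. This also removes the stray word in the PR limit.
2. State in both places how exactly 5% blasts is classified, so that CR and PR adjoin. Copying Appendix 11 alone would carry its gap into section 9.1.
3. Reconcile both with the list in section 10.2 of categories that count as overall response.

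The cost is protocol wording. Sample size, visits and assessments do not change.

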24.11.2 Partial remission (PR)

All of the CR criteria (if abnormal prior to treatment), except:

Bone marrow evaluation: Blasts decreased by $\geq 50\%$ over pretreatment but still > 5%. Cellularity and morphology are not relevant.

24.11.3 Marrow CR

- Bone marrow: $\leq 5\%$ myeloblasts and decrease by $\geq 50\%$ over pretreatment
- Peripheral blood: if HI responses, they will be noted in addition to marrow CR

24.11.4 Stable disease

Failure to achieve at least a PR, but with no evidence of progression for > 8 weeks.

24.11.5 Failure

Death during treatment or disease progression characterized by worsening of cytopenias, increase in percentage of bone marrow blasts, or progression to a more advanced MDS FAB subtype than pretreatment.

24.11.6 Relapse (following a CR or PR)

One or more of the following:

- Return to pretreatment bone marrow blast percentage.
- Decrement of $\geq 50\%$ from maximum remission response levels in granulocytes or platelets.
- Reduction in Hgb concentration by ≥ 1.5 g/dL or transfusion dependence.

24.11.7 Disease progression

For patients with:

- Less than 5% blasts: $\geq 50\%$ increase in blasts to $> 5\%$ blasts
- 5%-10% blasts: $\geq 50\%$ increase to $> 10\%$ blasts
- 10%-20% blasts: $\geq 50\%$ increase to $> 20\%$ blasts
- 20%-30% blasts: $\geq 50\%$ increase to $> 30\%$ blasts

Any of the following:

- At least 50% decrement from maximum remission/response in granulocytes or platelets
- Reduction in Hgb by ≥ 2 g/dL
- Transfusion dependence

24.11.8 Cytogenetic response

Requires 20 analyzable metaphases when using conventional cytogenetic techniques.

- Complete Cytogenetic Response: Disappearance of the chromosomal abnormality without appearance of new ones.
- Partial Cytogenetic Response: At least 50% reduction of the chromosomal abnormality.

24.11.9 Survival

Endpoints:

Overall: death from any cause

Event free: failure or death from any cause

PFS: disease progression or death from MDS

DFS: time to relapse

Cause-specific death: death related to MDS

To convert hemoglobin from grams per deciliter to grams per liter, multiply grams per deciliter by 10.

MDS indicates myelodysplastic syndromes; Hgb, hemoglobin; CR, complete remission; HI, hematologic improvement; PR, partial remission; FAB, French-American-British; AML, acute myeloid leukemia; PFS, progression-free survival; DFS, disease-free survival.

*Dysplastic changes should consider the normal range of dysplastic changes.

‡In some circumstances, protocol therapy may require the initiation of further treatment (eg, consolidation, maintenance) before the 4-week period. Such patients can be included in the response category into which they fit at the time the therapy is started. Transient cytopenias during repeated chemotherapy courses should not be considered as interrupting durability of response, as long as they recover to the improved counts of the previous course.

